### I. Background and Significance:

Major depression is both common and burdensome, affecting over 15 million Americans in 2010 and costing over 210 billion dollars. Moreover, existing treatments for depression often do not achieve remission. Only a third of patients will achieve remission with their first antidepressant trial, and up to a third will not achieve remission even after multiple medication trials. Patients who do not respond to at least one antidepressant trial can be deemed treatment-resistant (although treatment-resistance exists along a continuum). It is possible that treatment resistant depression (TRD) may require novel treatment approaches. Many of the most frequently used pharmacologic treatments for depression target the monoamine systems or are hypothesized to exert an effect by affecting monoamine function, and other drugs under evaluation are generally focused on other neurotransmitter systems. A focus on other systems may yield additional treatment options for treatment-resistant depression.

Increasingly, converging lines of evidence support a role for inflammation in the pathogenesis of depression. Elevations in the inflammatory markers C-reactive protein (CRP) and interleukin-6 (IL-6) are found in patients with depression as compared to normal controls. Elevated levels of CRP can also predict the onset of depression, suggesting a role for inflammation in its pathogenesis. Tumor necrosis factor  $\alpha$  (TNF- $\alpha$ ), too, has been demonstrated to be elevated in major depression. When healthy volunteers are given endotoxin infusions, which stimulate the release of cytokines, the cytokine levels were associated with the development of mood disorder symptoms. Administration of exogenous cytokines including TNF- $\alpha$  and interferon- $\alpha$  (IFN-  $\alpha$ ) have produced classical symptoms of depression in previously mood-stable individuals. Finally, antidepressant treatment has been demonstrated to reduce levels of IL-6 and CRP in depressed patients, and a lack of response to treatment has been associated with persistent elevations in these inflammatory markers. Taken together, the above suggests a role for inflammation in the development of depression and given this, investigation of anti-inflammatory agents in the treatment of depression is indicated.

Many existing anti-inflammatory treatments are developed for the treatment of autoimmune disorders and carry risks of serious side effects including that of immunosuppression. These treatments can also be costly. There has been some interest, therefore, in anti-inflammatory agents with a more moderate side effect profile and lower cost. NSAIDs fit these criteria and have been previously evaluated for their effect in depression. Thus far studies have demonstrated significant heterogeneity across a number of domains including methodology, patient population, and medication used, and results have been inconsistent. Studies examining at the effect of NSAIDs on pain in patients with medical illness have found concomitant improvements in depression symptoms. In a population of osteoarthritis patients with depressive symptoms, treatment with NSAIDs (ibuprofen, naproxen, and celecoxib) compared favorably with placebo, showing a trend toward greater reduction in depressive symptoms. In patients with breast cancer and mild to moderate depression, benefits were also found

from treatment with NSAIDs, with patients receiving celecoxib showing significantly greater improvement in depression scores than those receiving diclofenac.

Evaluation of the effect of anti-inflammatory treatment in patients with depression has not been limited to those with medical illness. As pain and disease effects could be major contributors to depressed mood, some studies have been done to investigate anti-inflammatory efficacy in patients with major depression without major medical comorbidities. In one randomized, double-blind, placebo controlled study celecoxib was given to patients with major depression as an adjunctive treatment to the antidepressant reboxetine (a selective norepinephrine reuptake inhibitor). A much greater improvement in depression symptoms was shown among those receiving celecoxib as the adjunct. In a similar study utilizing celecoxib as an adjunctive agent to antidepressant treatment with fluoxetine, those patients given celecoxib saw significantly greater improvement. In a follow-up study celecoxib used as an adjunctive agent to treatment with sertraline demonstrated both significantly improved depression scores in the celecoxib group and also significantly greater reductions in the inflammatory biomarker IL-6, with significant correlations observed between Hamilton Depression Rating Scale (HAM-D) scores and IL-6 levels. Two meta-analyses of the use of celecoxib as an adjunctive treatment for patients with depression both found in favor of its use. Unfortunately, COX-2 inhibitors such as celecoxib carry an increased risk of ischemic cardiovascular disease, to the extent that related medications rofecoxib and valdecoxib have been withdrawn from most markets. Some analyses support the idea that salicylates and COX-2 inhibitors may separate from other NSAIDs in their relationship to antidepressant response. Given that salicylates like aspirin are ubiquitous, with low cost and a safety profile in long-term use that is well-known, there would be an advantage to the use of salicylates in depression if indeed they prove effective.

There may be other advantages as well: aspirin, unlike the selective agent celecoxib, is technically a ‘nonselective’ inhibitor of cyclooxygenase, although it in fact more potently inhibits COX-1 than COX-2. As there is some evidence that COX-2 has anti-inflammatory and neuroprotective activities in the brain, inhibiting it may not be the optimal target for antidepressant treatments.

Cyclooxygenase inhibition weighted towards COX-1 could be more effective. In an animal model of depression (rats subjected to chronic mild stress and showing depression-like behavior), treatment with aspirin – both alone and in combination with the antidepressant amitriptyline – was associated with a reduction in depression-like behaviors (e.g. increased sucrose preference). In rats with depression-like behaviors that did not respond to fluoxetine, adjunctive aspirin treatment significantly improved the behaviors. In humans, while aspirin treatment in conjunction with fluoxetine did not separate from fluoxetine-only treatment in terms of HDRS score, the combination did produce a significantly greater reduction in oxidative stress parameters, which has been suggested to be associated with depression severity. Furthermore, an open-label assessment of aspirin in combination with an SSRI in patients who had not responded to the SSRI alone found favorable response and remission rates, and a rapid improvement in HDRS scale in a ‘responder’ subgroup (that was sustained until the conclusion of the study). This was interpreted as aspirin exerting an accelerating effect of antidepressant action, consistent with prior preclinical findings. Some population data supports an antidepressant effect for aspirin as well: in a nested case-control study of adult men exposure to aspirin and statins were associated with a significant reduction in the likelihood of mood disorders and in a retrospective cohort study exposure to these agents reduced the risk for de novo mood disorders. The potential for clinical effect of aspirin augmentation is of importance, and while a protocol for a randomized clinical trial (RCT) of aspirin treatment in bipolar depression has been described, an RCT of aspirin in treatment-resistant unipolar depression is lacking. Given the large and clinically significant reduction in depression scores in the previous open-label trial of aspirin as an adjunct to antidepressant treatment, we propose to pursue an RCT to

see if the effect is borne out against placebo augmentation. Moreover, we hope to identify whether a specific pattern of biomarker elevation can predict antidepressant response to aspirin, since previous work has suggested that anti-inflammatory treatments in depression may have efficacy only in those patients with high inflammatory biomarkers prior to the treatment. This could provide a biomarker signature that identifies a sub-group of patients who would benefit from aspirin augmentation treatment.

## **II. Specific Aims:**

The primary aims of this study are:

**Aim 1:** To evaluate the clinical effect of aspirin augmentation on depression.

**Aim 1a:** To examine the effect of aspirin augmentation on depression symptoms (as measured by the Hamilton Depression Rating Scale) in comparison to placebo augmentation of antidepressant treatment.

**Aim 1b:** To examine the effect of aspirin augmentation on the rapidity of change in depression symptoms (as measured by the Hamilton Depression Rating Scale).

**Aim 2:** To assess with Luminex immunoassay the inflammatory profile of the blood of the aspirin augmentation responders compared with the non-responders.

**Aim 2a:** To determine whether elevated serum inflammatory cytokines IL-6 and TNF- $\alpha$  at study initiation are associated with treatment response to aspirin.

**Aim 2b:** To determine whether serum inflammatory cytokines IL-6 and TNF- $\alpha$  are lower in the augmentation responders group after treatment than in the augmentation non-responders group after treatment.

**Aim 2c:** To determine whether the ratios of TNF- $\alpha$ :IL-10 and IL-6:IL-10 are associated with treatment response versus non-response.

**Aim 3:** To evaluate in an exploratory fashion whether other cytokines/chemokines or immune gene expression patterns at study initiation are associated with subsequent antidepressant response to aspirin.

**Aim 3a:** To assess the panel of 60 cytokines/chemokines in the aspirin augmentation responders compared with the non-responders for potential contributions to treatment responsiveness. This analysis is exploratory.

**Aim 3b:** To assess with Fluidigm technology the blood of the aspirin augmentation responders compared with the non-responders for RNA from three flow sorted subsets of activated memory CD4 $^{+}$  (CD3 $^{+}$ CD44 $^{\text{hi}}$ ), and CD8 $^{+}$  (CD3 $^{+}$ CD44 $^{\text{hi}}$ ) T cells, as well as CD14 $^{+}$  monocytes. 96 T cell or monocyte-specific genes for pro-inflammatory, anti-inflammatory, chemokine, chemokine receptor, and signaling molecules will be measured. This analysis is exploratory.

**Aim 4:** To collect samples for eventual detailed immunologic characterization including antigen arrays and microRNAs.

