## **Hypotheses:**

Peripheral inflammatory mediators are differentially expressed in sub-populations of depressed patients, and such differences may represent indicators of responsiveness to anti-inflammatory treatment approaches.

**1a:** That aspirin augmentation will decrease HDRS scores versus placebo augmentation, and that a responder subgroup within the aspirin augmentation group will account for most of this signal.

**1b:** That aspirin augmentation will exert most of its clinical effect (steepest slope of change in HDRS) during the first 4 weeks of treatment.

**2:** That the serum inflammatory profile of the aspirin augmentation responders differs from the non-responders.

**2a:** That elevated IL-6 and TNF- $\alpha$  at study initiation will be associated with treatment response to aspirin.

**2b:** That IL-6 and TNF- $\alpha$  will be lower in the augmentation responders group versus the non-responders group after treatment.

**2c:** That higher ratios of TNF- $\alpha$ :IL-10 and IL-6:IL-10 will be associated with greater treatment response to aspirin.

**3:** That there will be different patterns of immunologic activation between treatment responders and non-responders, and within the treatment-responders group before and after treatment with aspirin.

**3a:** That the cytokines/chemokines assessed will show a different pattern of elevations in the aspirin-responder versus the aspirin non-responder group pre-treatment, and that the aspirin-responder group will show a differential pattern post- versus pre-treatment.

**3b:** That the peripheral inflammatory transcriptome will show altered patterns of immune gene expression in the aspirin-responder versus the aspirin non-responder group pre-treatment, and that the aspirin-responder group will show a differential pattern of gene expression post- versus pre-treatment.

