## **VI. Biostatistical Analyses:**

The baseline data to be collected and analyzed include: subject age at enrollment, gender, age of depression onset, number of previous depressive episodes, HDRS. HDRS will be repeated at the subsequent study visits for analysis. Cytokine levels will also be analyzed at the initial and final visits. The planned study end-point is at eight weeks after initiation, and is not based on any pre-determined treatment response. Exploratory analysis of the immunologic profiling data will be performed as well, with a goal to detect within-subject changes over the course of the study and to discern any differences between non-responders and responders.

Baseline measurements for continuous variables (e.g., age of onset, current age) will be assessed by t-test. Categorical measurements, such as gender, will be compared with Fisher's exact test or chi-square as appropriate. For the primary study outcome, the change in HDRS in the treatment versus control groups will be evaluated with analysis of covariance (ANCOVA), with initial HDRS score as a covariate.

Power calculations were based on a prior open-label trial of salicylic acid as an augmentation agent to fluoxetine, which found an average 15-point drop in HDRS score over a 4-week trial. To be conservative, we are assuming a much smaller effect size, and so this study is powered to detect a 3-point difference in HDRS score, a difference which is deemed to be clinically significant. 29 participants per group are required to detect this clinically significant difference assuming .80 power and a two-sided alpha of 0.05. Assuming a non-completion rate of approximately 20%, customary in clinical trials of antidepressants, we will enroll 74 subjects, anticipating 60 completers.

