Secondary outcomes will include the response of inflammatory biomarkers in treatment responders v. treatment non-responders at 8 weeks and the degree of biomarker association with antidepressant response. For this, the association of IL-6 and TNF- $\alpha$  at V1 with change in HDRS from V1 to V4 in the aspirin treated group versus the placebo treated group will be evaluated with an analysis of covariance (ANCOVA) model. This model will include three variables: treatment condition (aspirin versus placebo), baseline IL-6 or TNF- $\alpha$  level, and an interaction term (baseline cytokine value x treatment). A similar analysis of change in HDRS scores will be performed to assess the interaction of baseline TNF- $\alpha$  to IL-10 and IL-6 to IL-10 ratios by treatment condition. All applicable tests will be two-tailed with an alpha set at 0.05.

For our exploratory analysis of the full panel of 60 cytokines and chemokines, we expect to perform 60 comparisons and plan to use a false discovery rate approach. The interaction of the baseline value of each cytokine or chemokine with treatment condition will be evaluated. The interaction  $p$  values will be converted to FDR *adjusted p* values and ordered from smallest to largest. A cut point of 10% will be used to control the false discovery rate and to identify a subset of values that will be presumed to be biologically relevant. A similar procedure will be carried out for analysis of the 96 immune genes. All analyses were designed in consultation with a biostatistician.

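### Aim 2b compares week-8 IL-6 and TNF-alpha in responders and non-responders without the visit-1 level, so the baseline gap predicted by Hypothesis 2a can attenuate, hide or reverse a real fall

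*Combined protocol and SAP*

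**What the plan says.** Section II, Aim 2b, asks whether serum IL-6 and TNF-alpha "are lower in the augmentation responders group after treatment than in the augmentation non-responders group after treatment". Hypothesis 2b repeats the contrast: the two cytokines "will be lower in the augmentation responders group versus the non-responders group after treatment". Both are about the level at the end of treatment. Neither mentions a change or a baseline covariate.

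Hypothesis 2a says that elevated IL-6 and TNF-alpha "at study initiation will be associated with treatment response to aspirin". The size of that baseline difference is not given.

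Section VI lists as a secondary outcome "the response of inflammatory biomarkers in treatment responders v. treatment non-responders at 8 weeks", which can be read as a level or as a change. The model that follows has change in HDRS as its outcome: "This model will include three variables: treatment condition (aspirin versus placebo), baseline IL-6 or" TNF-alpha, and their product. It serves Aim 2a and, with the ratios substituted, Aim 2c. No model in section VI has a week-8 cytokine as its outcome.

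Three passages bear on change over time:
- Section VI: "Cytokine levels will also be analyzed at the initial and final visits".
- Section VI, for the exploratory immunologic profiling: "a goal to detect within-subject changes over the course of the study and to discern any differences between non-responders and responders".
- Hypothesis 3a, on the exploratory panel: "the aspirin-responder group will show a differential pattern post- versus pre-treatment". Section V (Study Visit 1) lists IL-6 and TNF-alpha among the 60 analytes.

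None of the three gives a model or refers to Aim 2b.

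**The concern.** A person's cytokine levels eight weeks apart are normally correlated. If responders start higher, as 2a predicts, some or all of that excess is still there at week 8. The raw contrast is then the carried-over excess minus whatever fall goes with response. On that contrast, 2a and 2b can both be met only if responders start above non-responders and finish below them.

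This is a named secondary outcome with roughly 30 aspirin completers. Analysed as the aim is worded, it could show no difference, or a difference in the wrong direction, when levels in responders had in fact dropped. The trial would then misreport whether response goes with reduced inflammation, even though the visit-1 values needed to avoid this are already collected.

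**Working it through.** **The plan's own figure.** No sample size or power is stated for 2b. The 29 per group in section VI is for a 3-point HDRS difference and does not bear on this point. It serves only to fix the number of completers: 29/(1 − 0.20) = 36.25, so 37 per group and 74 in all; 74 × 0.80 = 59.2, against 60 stated. That is about 30 completers on aspirin.

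**Inputs from the documents.** About 30 aspirin completers; two-sided alpha 0.05 (section VI); responders higher at baseline (Hypothesis 2a).

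**Assumed inputs, none in the documents.** 12 responders and 18 non-responders; log cytokine with SD 1; correlation r = 0.5 to 0.7 between visit 1 and week 8; baseline gap d = 0.5 to 0.8 SD; fall f = 0.8 SD in responders only.

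**Two data models.** G = 1 for responders; e and u are independent standard normal errors. In both, V1 = dG + e.
- Regressing gap (the excess shrinks toward a common mean): V4 = r·V1 − fG + √(1 − r²)·u.
- Stable gap (responders are a subgroup with its own higher level): V4 = dG + r·e − fG + √(1 − r²)·u.

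**Expected responder minus non-responder difference**

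| Analysis | Regressing gap | Stable gap |
|---|---|---|
| Raw week 8 | r·d − f | d − f |
| Change from baseline | −f − (1 − r)·d | −f |
| ANCOVA on V1 | −f | −f + (1 − r)·d |

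With f = 0.8:
- Raw, regressing gap: from 0.5 × 0.5 − 0.8 = −0.55 to 0.7 × 0.8 − 0.8 = −0.24.
- Raw, stable gap: from 0.5 − 0.8 = −0.30 to 0.8 − 0.8 = 0.
- ANCOVA, stable gap: from −0.8 + 0.3 × 0.5 = −0.65 to −0.8 + 0.5 × 0.8 = −0.40.

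The raw contrast is therefore zero or of the wrong sign only when f ≤ r·d (regressing) or f ≤ d (stable). A larger fall is attenuated, not hidden.

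**Simulated chance of a significantly lower result in responders, f = 0.8** (two-sided 0.05; repeat runs differ by about one percentage point)

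| Analysis | Regressing gap | Stable gap |
|---|---|---|
| Raw week 8 | about 9–31% | about 2–11% |
| ANCOVA on V1 | about 59–78% | about 20–60% |

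One case within the range, regressing gap, r = 0.6, d = 0.5: raw 26%, change 83%, ANCOVA 70%. Under the stable gap, change from baseline detects the fall in 54–77%. With no baseline gap at all, adjustment still raises detection from about 54% to 65–81%.

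**No true fall (f = 0), same gaps**
- Change score declares responders lower in 7–18% under the regressing gap, against a nominal 2.5% in that direction, and in 2.3–2.7% under the stable gap.
- ANCOVA declares responders lower in about 2.5% (regressing) and under 1% (stable). Under the stable gap it declares them higher in 8–19%.
- Raw declares responders higher in about 25–55% under the stable gap.

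**Other splits, stable gap.** With 15 v 15 and f = d = 0.8, raw detects the fall in 2–3%, ANCOVA in 20–48% and change in 56–78%. With d = 0.8 and f = 0.4, raw finds responders significantly higher in about 18%. With d = 0.4 and f = 1.2, raw power is about 56%, so a fall well above the gap is often still found. A 10 v 20 split gives the same pattern.

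**The case against.** Five points can be made on the other side.

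1. *Responders and non-responders are not randomised groups, so ANCOVA is not automatically right.* This stands. Hypothesis 2a and the introduction to the hypotheses, which speaks of sub-populations, fit a stable gap at least as well as a regressing one. With a stable gap, ANCOVA estimates −0.40 to −0.65 for a true −0.80, while the change score is unbiased. A reader might infer that only ANCOVA is valid and that change scores should be barred. The documents do not support that, because they do not say which data model holds.

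2. *A real fall is not always hidden.* This stands. Full masking needs a fall no larger than the carried-over gap, and the documents give neither quantity.

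3. *Aim 2b asks a legitimate descriptive question about the end-of-treatment state, and 2a and 2b together predict a crossover.* It is tempting to call the two hypotheses contradictory. They are not: a crossover is demanding but coherent. The difficulty is in reading the raw contrast as evidence about a reduction.

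4. *Change is addressed elsewhere.* Partly true. Section VI's within-subject goal and Hypothesis 3a mean that a fall need not go unseen in the trial. Both are exploratory, have no model and are not tied to 2b, so they do not repair the secondary outcome.

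5. *Section VI chooses no test for 2b, so the point is only missing detail.* It is true that no raw test is named in section VI. But the aim and the hypothesis both state the after-treatment contrast, and an analyst following them would compare week-8 levels.

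**Conclusion.** The point holds in a conditional form. As worded, 2b takes no account of the visit-1 level, section VI does not supply it, and Hypothesis 2a predicts a gap in the direction that works against 2b. The raw contrast can attenuate, hide or reverse a real fall.

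Under the assumed inputs, the raw test detects a 0.8 SD fall in about 2% to 31% of trials and the baseline-adjusted test in about 20% to 78%. Adjustment is better under both data models, so the criticism of the raw test does not depend on which is true. The size does: the responder split, correlation, gap and fall are all assumptions.

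The choice between ANCOVA and change from baseline is less clear-cut. ANCOVA is conservative for claiming lower levels if the gap is stable; the change score is prone to regression to the mean if it is not. For a claim that response goes with reduced inflammation, ANCOVA is the more defensible main analysis, with change reported beside it. This should be corrected before analysis; it does not touch the primary outcome.

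**What to change.** Add to section VI, and reword Aim 2b and Hypothesis 2b to match:

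- Week-8 IL-6 and TNF-alpha are each compared between aspirin responders and non-responders by ANCOVA, with the visit-1 value of the same cytokine as covariate. Hypothesis 2b is supported if the adjusted week-8 level is lower in responders.
- Change from baseline is a prespecified sensitivity analysis. If the two analyses disagree, the report says so and notes that the groups are not randomised: ANCOVA understates a fall when the baseline gap is stable, and the change score overstates it when the gap regresses to the mean.
- The raw week-8 comparison is descriptive only.

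The cost is one degree of freedom and one added analysis. No further samples or subjects are needed, since cytokines are already measured at the first and last visits. The comparison also needs a numeric definition of responder, which the documents do not give; that is a separate matter, but the 2b text cannot be applied without it.
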